# 9.0 CRITERIA FOR RESPONSE

# Major hematologic response (MaHR): The detailed definition of MaHR is listed below.

Major hematologic response (MaHR) defined as either:				
Complete Hematologic Response (CHR)	No Evidence of Leukemia (NEL)			

 
White blood count (WBC)         
 
institutional upper limit             of normal (ULN)
 
 
 
Absolute neutrophil             count (ANC)             ≥1000/mm^3
 
Platelets ≥100,000/mm^3
 
Platelets ≥100,000/mm^3
 
No blasts or promyelocytes             in peripheral blood
 
Bone marrow blasts ≤5%
 
<5% myelocytes plus             metamyelocytes in             peripheral blood
 
Basophils <5% in             peripheral blood
 
No extramedullary             involvement (including             no hepatomegaly or             splenomegaly)
 
	
 
WBC ≤ institutional ULN
 
No blasts or promyelocytes in peripheral blood
 
Bone marrow blasts ≤5%
 
<5 % myelocytes plus metamyelocytes in peripheral blood
 
Basophils <5% in peripheral blood
 
No extramedullary involvement (including no hepatomegaly or splenomegaly)
 
At least one of the following: (i) 20,000/mm^3 ≤ platelets < 100,000/mm^3 (ii) 500/mm^3 ≤ ANC < 1000/mm^3
 
			

# **Complete Response (CR):**

Disappearance of all clinical and/or radiologic evidence of disease

Neutrophil count  $\ge 1.0 \ge 10^{9}/L$ 

Platelet count  $\geq 100 \ge 10^{9}$ /L Normal bone marrow differential ( $\leq 5\%$  blasts) No extra-medullary leukemia

## **Complete Remission without Incomplete Blood Count Recovery (CRi):**

CR except for ANC  $< 1.0 \text{ x } 10^{9}/\text{L}$  and/or platelets  $< 100 \text{ x } 10^{9}/\text{L}$ 

## **Partial Remission (PR):**

Blood count recovery as for CR, but with a decrease of at least 50% in the percentage of marrow blasts to >5% to 25% in the bone marrow.

## **10.0 ADVERSE EVENT REPORTING**

## 10.1 Leukemia-specific Adverse Event Recording and Reporting Guidelines

These guidelines serve to bring the Department of Leukemia in compliance with the institutional policy on Reporting of Serious Adverse Events-definition of expected AE-"

Adverse event is any untoward medical occurrence that may present during treatment with a pharmaceutical product but which does not necessarily have a causal relationship with this treatment.

Adverse drug reaction is a response to a drug which is noxious and unintended and which occurs at doses normally used in man for prophylaxis, diagnosis, or therapy of disease or for the modification of physiologic function.

Assessing causal connections between agents and disease is fundamental to the understanding of adverse drug reactions. In general, a drug may be considered a contributory cause of an adverse event if, had the drug not been administered, 1) the event would not have happened at all, 2) the event would have occurred later than it actually did, or 3) the event would have been less severe.

The Investigator or physician designee is responsible for verifying and providing source documentation for all adverse events and assigning the attribution for each event for all subjects enrolled on the trial.

**10.1.1** PDMS/CORe will be used as the electronic case report form for this protocol. Adverse events will be documented in the medical record and entered into PDMS/CORe.

- **10.1.2** Adverse Events (AEs) will be evaluated according to the CTCAE version 4.0 and documented in medical record. All AE's regardless of grade and attribution will be collected on toxicity logs; however, unexpected and related AE's of all grades will be entered into CORe. Only unexpected AEs, any grade, will be recorded in the Case Report Form (CRF). Expected events during leukemia therapy are:
  - **10.1.2.1** Myelosuppression related events (due to disease or leukemia therapy)
    - **10.1.2.1.1** Febrile or infection episodes not requiring management in the intensive care unit
    - **10.1.2.1.2** Epistaxis or bleeding except for catastrophic CNS or pulmonary hemorrhage
    - **10.1.2.1.3** Anemia, neutropenia, lymphopenia, thrombocytopenia, leukopenia
  - **10.1.2.2** Disease related events
    - **10.1.2.2.1** Symptoms associated with anemia (fatigue, weakness, shortness of breath)
    - **10.1.2.2.2** Electrolyte abnormalities (sodium, potassium, bicarbonate, CO2, magnesium)
    - **10.1.2.2.3** Chemistry abnormalities (LDH, phosphorus, calcium, BUN, protein, albumin, uric acid, alkaline phosphatase, glucose)
    - 10.1.2.2.4 Coagulation abnormalities
    - **10.1.2.2.5** Disease specific therapy (induction, maintenance, salvage, or stem cell therapy)
    - 10.1.2.2.6 Alopecia
    - 10.1.2.2.7 Bone, joint, or muscle pain
    - **10.1.2.2.8** Liver function test abnormalities associated with infection or disease progression
    - 10.1.2.2.9 Disease progression
    - **10.1.2.2.10** Abnormal hematologic values
  - **10.1.2.3** General therapy related events
    - **10.1.2.3.1** Catheter related events
    - **10.1.2.3.2** Renal failure related to tumor lysis syndrome or antibiotic/ antifungal therapy
    - 10.1.2.3.3 Rash related to antibiotic use
  - **10.1.2.4** Hospitalization for the management of any of the above expected events
- **10.1.3** Abnormal hematologic values will not be recorded on the case report form. For abnormal chemical values, the apogee or nadir (whichever is appropriate) will be reported per course on the case report form.

- **10.1.4** All events that are not listed as expected in section 10.1.2 will be collected for the purpose of grading, and determining attribution to study drug by the PI.
- 10.1.5 Serious Adverse Event Reporting (SAE)

An adverse event or suspected adverse reaction is considered "serious" if, in the view of either the investigator or the sponsor, it results in any of the following outcomes:

- Death
- A life-threatening adverse drug experience any adverse experience that places the patient, in the view of the initial reporter, at immediate risk of death from the adverse experience as it occurred. It does not include an adverse experience that, had it occurred in a more severe form, might have caused death.
- Inpatient hospitalization or prolongation of existing hospitalization.
- A persistent or significant incapacity or substantial disruption of the ability to conduct normal life functions.
- A congenital anomaly/birth defect.

Important medical events that may not result in death, be life-threatening, or require hospitalization may be considered a serious adverse drug experience when, based upon appropriate medical judgment, they may jeopardize the patient or subject and may require medical or surgical intervention to prevent one of the outcomes listed in this definition. Examples of such medical events include allergic bronchospasm requiring intensive treatment in an emergency room or at home, blood dyscrasias or convulsions that do not result in inpatient hospitalization, or the development of drug dependency or drug abuse (21 CFR 312.32).

- Important medical events as defined above, may also be considered serious adverse events. Any important medical event can and should be reported as an SAE if deemed appropriate by the Principal Investigator or the IND Sponsor, IND Office.
- All events occurring during the conduct of a protocol and meeting the definition of a SAE must be reported to the IRB and IND Office in accordance with the timeframes and procedures outlined in "The University of Texas M. D. Anderson Cancer Center Institutional Review Board Policy for Investigators on Reporting Unanticipated Adverse Events for Drugs and Devices". Unless stated otherwise in the protocol, all SAEs, expected or unexpected, must be reported to the IND Office, regardless of attribution (within 5 working days of knowledge of the event).

# "Serious Adverse Event Reporting (SAE) for M. D. Anderson-Sponsored IND Protocols":

- All life-threatening or fatal events, that are unexpected, and related to the study drug, must have a written report submitted within 24 hours (next working day) of knowledge of the event to the Safety Project Manager in the IND Office.
- Unless otherwise noted, the electronic SAE application (eSAE) will be utilized for safety reporting to the IND Office and MDACC IRB.
- Serious adverse events will be captured from the time of the first protocol-specific intervention, until 30 days after the last dose of drug, unless the participant withdraws consent. Serious adverse events must be followed until clinical recovery is complete and laboratory tests have returned to baseline, progression of the event has stabilized, or there has been acceptable resolution of the event.
- Additionally, any serious adverse events that occur after the 30 day time period that are related to the study treatment must be reported to the IND Office. This may include the development of a secondary malignancy.

## **Reporting to FDA:**

• Serious adverse events will be forwarded to FDA by the IND Sponsor (Safety Project Manager IND Office) according to 21 CFR 312.32.

It is the responsibility of the PI and the research team to ensure serious adverse events are reported according to the Code of Federal Regulations, Good Clinical Practices, the protocol guidelines, the sponsor's guidelines, and Institutional Review Board policy.

## **Investigator Communication with Supporting Companies:**

Any individual expedited SAE reports required by the FDA will be reported to Pfizer within 24 hours of first awareness of the event (immediately if the event is fatal or life-threatening), Principal Investigator will report to Pfizer by facsimile any Serious Adverse Event as soon as it is determined to meet the definition. Principal Investigator will report SAEs using one of the following forms: (1) an FDA MEDWATCH form, (2) a CIOMS form, (3) an Investigator-Initiated Research Serious Adverse Event (IIR SAE) form, or (4) any other form prospectively approved by Pfizer. The *Reportable Event Fax Cover Sheet* provided by Pfizer must also be included with each SAE submitted.

# 11.0 STATISTICAL CONSIDERATIONS

# 11.1 Endpoints

## **11.1.1 Primary Endpoints:**

Phase I:

1. MTD of bosutinib in combination with inotuzumab ozogamicin in patients with Ph+ ALL and CML in lymphoid blast phase that express CD22

Phase II:

2. Major hematologic response (MaHR) for relapsed ph+ALL and CR/CRi for newly diagnosed Ph+ ALL or CML-LBC with age≥60.

# **11.1.2 Secondary Endpoints:**

Phase I:

1. Overall MaHR

2. Duration of response and overall survival

Phase II:

- 3. Incidence and severity of adverse events
- 4. Duration of response and overall survival

# 11.2 Sample size

This will be a single arm, single center, open label study of bosutinib in combination with inotuzumab ozogamicin in patients with Ph+ ALL and CML in lymphoid blast phase that express CD22. There are two parallel cohorts of patients: relapsed ph+ALL and newly diagnosed Ph+ ALL or CML-LBC with age $\geq$ 60.

Sample size – Up to 18 patients will be enrolled in phase I part of the study for each cohort. Therefore, there will be a maximum of 36 patients, 18 patients per cohort in phase I part. A total of 56 patients will be enrolled in phase II with 28 patients for each patient cohort: relapsed ph+ALL and newly diagnosed Ph+ ALL or CML-LBC with age  $\geq 60$ . The 6 patients treated at the MTD from the phase I dose cohort will be included in the phase 2 part for each cohort. Therefore, the maximum sample size is 36 in phase I + 44 in phase II = 80.

# Phase I

Bosutinib will be dose-escalated in a standard 3+3 study design separately for two cohorts (relapsed ph+ALL and newly diagnosed Ph+ ALL or CML-LBC with age  $\geq$ 60). Patients will be entered sequentially to each dose level. Three combination dose levels are defined. The starting dose is dose 1. If none of the first 3 patients at a dose level experience first cycle dose-limiting toxicity (DLT), new patients may be entered at the next higher dose level. If 1 of 3 patients experience first cycle DLT, up to 3 more patients are started at that same dose level. If 1 of 6 experience DLT, then new patients may be entered at the next higher dose level. If 2 or more

experience first cycle DLT, no further patients are started at that dose. The MTD is the highest dose level in which <2 patients of 6 develop first cycle DLT. Detailed dose escalation rules are described in the following section. A maximum of 18 patients will enroll in the phase I study. DLT definition is provided in Section 4.1.2.

Number of Patients with	Decision	
DLT at a Dose Level		
0 of 3	Escalate and evaluate in 3 subsequent patients.	
1 of 3	Enroll 3 additional subjects at this dose level.	
	The MTD has been exceeded. Dose escalation will stop and this	
	level will be declared the maximum administered dose. Evaluate	
>/=2 of 3	3 additional patients at the prior dose level if only three were	
-1-2 81 3	treated at that dose previously.	
	An interim dose may be explored if the increments between	
	maximally administered dose and the next lower dose is $>50\%$ .	
1 of 6	Escalate dose and evaluate in 3 subsequent patients.	
=1 out of 6 at the Highest</td 	Dose Below the Maximum	This is the MTD.	
Administered Dose		
	The MTD has been exceeded. Dose escalation will stop and this	
	level will be declared the maximum administered dose. Evaluate	
>/=2  of  6	3 additional patients at the prior dose level if only three were	
>/-2 81 8	treated at that dose previously.	
	An interim dose may be explored if the increments between	
	maximally administered dose and the next lower dose is $>50\%$ .	

Table 11.1 Dose-Escalation Decision Rules for 3+3 Escalation Schema is provided below:

## Phase II

Cohort 1: relapsed ph+ALL

Once the MTD (bosutinib 500mg dose level or lower,) is established, a phase II portion will commence. Patients will receive bosutinib per the dose established in the Phase I study. Patients will receive inotuzumab ozogamicin at the same dose and schedule as for the Phase I part of the study.

A total of 28 patients (including the 6 patients treated at the MTD from the phase I dose cohort) will be enrolled in the phase II portion of the study. The primary efficacy endpoint is MaHR during the study period of 4 cycles. We will employ Simon MinMax two-stage design. The target response rate will be 50% and a response rate of 30% or lower will be considered as not

having desired efficacy. With alpha of 0.1 and beta of 0.2, the first stage will require 12 patients. If there are 3 or fewer patients responded, the trial will be stopped. If 4 or more out of the first 12 patients respond, accrual will continue until a total of 28 patients have been enrolled. At the end of the study, if 12 or more patients out of 28 patients respond, the regimen will be considered active. With this design, the probability of early termination is 49% if the true response rate is only 30%.

The method of Thall, Simon, and Estey will be used to perform interim safety monitoring. We will assume a Beta (0.6, 1.4) prior distribution for the toxicity rate which in particular has mean of 30%. The toxicity is defined as any DLT at least possibly attributed to the study drug during the treatment period.

The following decision criteria will be applied continuously up to the 28 patient. The trial will be stopped early according to the following monitoring rule.

$$Pr\{toxicity rate > 30\% | data\} > 0.93$$

That is, if at any time during the study we determine that there is more than a 93% chance that the toxicity rate is more than 30% we will stop the study. The design software Multc Lean Desktop (version 2.1) developed by the Department of Biostatistics at M. D. Anderson Cancer Center (MDACC) was used to generate the toxicity stopping boundaries and the OC table. The stopping rule boundary is shown in table 12.2.

#patient	Stop the trial if there are this
	many toxicities total:
6	4-6
7-8	5-8
9-11	6-11
12-13	7-13
14-16	8-16
17-19	9-19
20-21	10-21
22-24	11-24
25-27	12-27
28	13-28

Table 11.2: Safety monitoring boundary

Table 11.3: the operating characteristics for safety monitoring

True toxicity Early Stopping P	bability Average number of patients treated
--------------------------------	---

0.2	0.03	27.4
0.25	0.09	26.5
0.3	0.19	25
0.35	0.34	22.7
0.4	0.53	19.8

#### Cohort 2: newly diagnosed Ph+ ALL or CML-LBC with age $\geq 60$ 

Patients in this cohort will be given the dosage of bosutinib in combination with inotuzumab ozogamicin that has been found to be safe in the relapsed patients. A total of 28 patients will be enrolled. The primary efficacy endpoint is CR/CRi during the study period of 4 cycles. Similar to the relapse cohort, we will employ Simon MinMax two-stage design. The target response rate will be 50% and a response rate of 30% or lower will be considered as not having desired efficacy. With alpha of 0.1 and beta of 0.2, the first stage will require 12 patients. If there are 3 or fewer patients responded, the trial will be stopped. If 4 or more out of the first 12 patients respond, accrual will continue until a total of 28 patients have been enrolled. At the end of the study, if 12 or more patients out of 28 patients respond, the regimen will be considered active. With this design, the probability of early termination is 49% if the true response rate is only 30%.

The method of Thall, Simon, and Estey will be used to perform interim safety monitoring. We will assume a Beta (0.6, 1.4) prior distribution for the toxicity rate which in particular has mean of 30%. The toxicity is defined as any DLT at least possibly attributed to the study drug during the treatment period.

The following decision criteria will be applied continuously up to the 28 patient. The trial will be stopped early according to the following monitoring rule.

 $Pr\{toxicity | rate > 30\% | data\} > 0.93$ 

That is, if at any time during the study we determine that there is more than a 93% chance that the toxicity rate is more than 30% we will stop the study. The design software Multc Lean Desktop (version 2.1) developed by the Department of Biostatistics at M. D. Anderson Cancer Center (MDACC) was used to generate the toxicity stopping boundaries and the OC table. The stopping rule boundary is shown in table 12.2.

 Table 11.2: Safety monitoring boundary

#patient	Stop the trial if there are this	
	many toxicities total:	

6	4-6
7-8	5-8
9-11	6-11
12-13	7-13
14-16	8-16
17-19	9-19
20-21	10-21
22-24	11-24
25-27	12-27
28	13-28

Table 11.3: the operating characteristics for safety monitoring

True toxicity	Early Stopping Probability	Average number of patients treated
0.2	0.03	27.4
0.25	0.09	26.5
0.3	0.19	25
0.35	0.34	22.7
0.4	0.53	19.8

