# 4.1.1.7 Dosing for the Frontline Ph+ ALL or CML-LBC Cohort

**Phase I dose-escalation Phase:** in the phase I portion of the study, frontline Ph+ ALL or CML-LBC patients will start therapy with bosutinib at 300 mg orally once daily. This dose has already been shown to be safe in the relapsed cohort (we have treated 3 patients with R/R ALL, and no DLT was noted at the 300mg dose level). Bosutinib will be dose-escalated in subsequent cohorts in a standard 3+3 study design.

Patients will receive inotuzumab ozogamicin as an intravenous infusion over approximately one hour on a weekly schedule ( $0.8 \text{ mg/m}^2$  IV day 1,  $0.5 \text{ mg/m}^2$  day 8 (±3 days), and 0.5 mg/m^2 day 15 (±3 days). A minimum of 6 days should be maintained between subsequent doses.

A cycle is defined as 28 days, however, start of cycle 2 may be delayed if the patient achieves a CR or CRi and/or to allow toxicity recovery.

Dose Level	Bosutinib (mg/day)	Inotuzumab ozogamicin IV (mg/m  ),
	orally once daily	repeat cycles every 3-4 weeks
-1	200	Day 1 - 0.8 mg/m 
		Day 8 - 0.5 mg/m 
		Day 15 - 0.5 mg/m 
1 (starting dose)	300	Day 1 - 0.8 mg/m 
		Day 8 - 0.5 mg/m 
		Day 15 - 0.5 mg/m 
2	400	Day 1 - 0.8 mg/m 
		Day 8 - 0.5 mg/m 
		Day 15 - 0.5 mg/m 
3	500	Day 1 - 0.8 mg/m 
		Day 8 - 0.5 mg/m 
		Day 15 - 0.5 mg/m 

For Cycles 2 to 6, if there are no peripheral blood blasts, the inotuzumab ozogamicin dose is reduced to  $1.5 \text{ mg/m}^2$  total but continues on a weekly schedule ( $0.5 \text{ mg/m}^2$  days 1, 8 (±3 days) and 15 (±3 days). A minimum of 6 days should be maintained between the doses. For patients who have achieved CR/CRi – the next cycle (cycle 2 and onwards) will begin when ANC ≥1.0, and platelet count ≥75. These count recovery guidelines could be modified based on treating physician assessment if determined to be in the best interest of the patient after discussion with study PI (e.g., if there is evidence of minimal residual disease).

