- **4.1.3** Cycle 1 is a 4 week cycle. However, cycle 2 may be started up to 1 week early if the patient has not achieved a CR or CRi and/or has persistent disease or rapidly proliferating disease, provided all drug-related toxicity has recovered to grade 1 or less. All subsequent cycles are 4 week cycles. Note: Subsequent cycles may start early if there is recovery of all toxicity related to the study drugs to grade 1 or less, but not earlier than day 21.
  - **4.1.3.1** Subsequent cycles may be delayed for recovery of toxicity. Delays in start of subsequent cycles greater than 8 weeks should be discussed with the principal investigator.
  - **4.1.3.2** If the peripheral counts do not recover (ANC <1  $x10^{9}/L$  and/or platelets <75  $x10^{9}/L$ ) but there is evidence of residual leukemia in the bone marrow, subsequent cycles can be administered at the discretion of the treating physician.
- **4.1.4** **Phase II Phase:** Once the MTD (or bosutinib 500 mg dose level, if MTD not exceeded at this level) is established in each cohort separately, a phase II portion will commence respectively for each cohort. For each cohort, the 6 patients at MTD from the phase I dose part will be enrolled in the phase II portion of the study.

Patients will receive bosutinib per the MTD established in the Phase I study. Patients will receive inotuzumab ozogamicin at the same dose and schedule as for the Phase I part of the study. For each cohort, a maximum of 28 patients (including the 6 patients at MTD from the phase I dose part) will be enrolled in the phase II portion of the study.

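### The frontline phase II text takes the bosutinib dose from relapsed patients, although the rest of the plan gives this cohort (age 60 or older) its own MTD

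*Combined protocol and SAP*

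**What the plan says.** The sentence at issue opens the Cohort 2 text in 11.2, under Phase II: patients "will be given the dosage of bosutinib in combination with inotuzumab ozogamicin that has been found to be safe in the relapsed patients". It then gives a total of 28 patients and does not mention the 6 patients carried over from phase I.

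Four other places set a different rule:

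- **4.1.4 (Phase II Phase):** the MTD, or 500 mg if that level is not exceeded, "is established in each cohort separately, a phase II portion will commence respectively for each cohort". It adds: "Patients will receive bosutinib per the MTD established in the Phase I study". Each cohort's maximum of 28 includes its 6 phase I patients at the MTD.
- **4.1.1.7 (frontline dosing):** the frontline cohort starts at 300 mg and then escalates through its own dose table. Of 300 mg it says "This dose has already been shown to be safe in the relapsed cohort", because "we have treated 3 patients with R/R ALL, and no DLT was noted at the 300mg dose level".
- **11.2, Phase I:** "Bosutinib will be dose-escalated in a standard 3+3 study design separately for two cohorts".
- **11.2, Sample size:** "The 6 patients treated at the MTD from the phase I dose cohort will be included in the phase 2 part for each cohort". It concludes: "Therefore, the maximum sample size is 36 in phase I + 44 in phase II = 80".

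The parallel Cohort 1 text in 11.2 gives both the dose from its phase I and the carry-over of 6. The Cohort 2 text gives neither.

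**The concern.** The sentence is a dosing instruction, and it can be read in two ways. On reading (a), the dose is the relapsed cohort's MTD. On reading (b), it is the 300 mg that 4.1.1.7 describes as safe in relapsed patients. Either way, it gives frontline patients a dose other than their own MTD whenever the two differ.

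On reading (a), if the relapsed MTD is the higher one, patients aged 60 or older are directed to a dose that their own escalation rejected or never reached. On reading (b), phase II stays at the starting dose even if the frontline escalation has cleared a higher level.

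The efficacy decision is also exposed. If the 6 carried-over patients are counted as 4.1.4 requires, while new patients are dosed by the Cohort 2 sentence, the Simon design pools two regimens.

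**Working it through.** **1. The stated maximum.** Inputs from 11.2, Sample size: up to 18 in phase I per cohort, 28 in phase II per cohort, 6 carried over per cohort.

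- As planned: 2×18 + 2×(28 − 6) = 36 + 44 = 80. The stated figure is reproduced.
- Frontline phase I run, but its 6 MTD patients not counted: 36 + 22 + 28 = 86.
- No frontline phase I at all: 18 + 22 + 28 = 68.

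Only a separate frontline phase I with carry-over gives 80, so the sample size agrees with 4.1.4.

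**2. The Simon design.** Stop at 3 or fewer of 12; active at 12 or more of 28. Exact binomial calculation gives early termination at a 30% response rate of 0.4925 (stated 49%), type I error 0.095 and power at 50% of 0.802. These figures hold. Carry-over could supply 6/12 = 50% of stage 1 and 6/28 = 21% of the full cohort.

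**3. How often the two rules give different doses.** I assumed DLT rates at 200/300/400/500 mg, the same in both cohorts, and enumerated the 3+3 in Table 11.1 exactly, starting at 300 mg and requiring 6 patients at the MTD. The relapsed run is conditioned on the 0 of 3 DLTs at 300 mg reported in 4.1.1.7. Runs with no tolerated dose (at most 2.3%) count as below 200 mg.

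For DLT rate p at a level, let f = (1−p)³ + 3p(1−p)⁵ (passes on the way up), q = (1−p)⁶ + 6p(1−p)⁵ (at most 1 of 6), and g = (1−p)³ + 3p(1−p)² (at most 1 of the next 3 after 0 of 3).

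Worked case, 10/15/25/40%: q200 = 0.886, f300 = 0.814, q300 = 0.776, g300 = 0.939, f400 = 0.600, q400 = 0.534, q500 = 0.233.

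- Relapsed MTD:
  - 500 mg: f400·q500 = 0.140
  - 400 mg: q400·(1 − q500) = 0.409
  - 300 mg: (1 − 0.140 − 0.409)·g300 = 0.423
  - 200 mg: 0.024; none: 0.003
- Frontline MTD:
  - 500 mg: f300·f400·q500 = 0.114
  - 400 mg: f300·q400·(1 − q500) = 0.333
  - 300 mg: q300·(1 − 0.140 − 0.409) = 0.350
  - 200 mg: 0.180; none: 0.023
- Same MTD: 0.140×0.114 + 0.409×0.333 + 0.423×0.350 + 0.024×0.180 + 0.003×0.023 = 0.305, so they differ in 0.695.
- Relapsed higher: 0.140×0.886 + 0.409×0.553 + 0.423×0.203 + 0.024×0.023 = 0.437.

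Reading (a), all curves (components rounded separately):

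| DLT rates (%) | MTDs differ | Relapsed higher | of which rejected in frontline | of which never tested in frontline |
|---|---|---|---|---|
| 10/15/25/40 | 0.695 | 0.437 | 0.289 | 0.148 |
| 5/10/20/30 | 0.699 | 0.396 | 0.253 | 0.142 |
| 5/10/15/20 | 0.643 | 0.368 | 0.203 | 0.165 |
| 5/5/10/15 | 0.471 | 0.249 | 0.160 | 0.088 |
| 2/3/5/8 | 0.195 | 0.103 | 0.069 | 0.033 |
| flat 5 | 0.135 | 0.081 | 0.031 | 0.050 |

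A milder flat 2% curve gives 0.025 differing and 0.015 with the relapsed MTD higher.

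Reading (b), position of the frontline MTD relative to 300 mg:

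| DLT rates (%) | Above | Equal | Below |
|---|---|---|---|
| 10/15/25/40 | 0.447 | 0.350 | 0.203 |
| 5/10/20/30 | 0.614 | 0.285 | 0.100 |
| 5/10/15/20 | 0.726 | 0.176 | 0.098 |
| 5/5/10/15 | 0.878 | 0.095 | 0.027 |
| 2/3/5/8 | 0.963 | 0.027 | 0.010 |
| flat 5 | 0.947 | 0.026 | 0.027 |

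**The case against.** The strongest reply is that the intended rule is not in doubt. Section 4.1.4 states it plainly, 11.2 supports it twice, and the total of 80 depends on it. The phase I rules also bar starting further patients at a level with 2 or more DLTs and stop escalation there. Any relapsed MTD above the frontline MTD is such a level or lies above one, so dosing there would breach two rules. Continuous toxicity stopping and individual dose reductions are further protection. On this view the sentence is an editorial slip, and the percentages mostly show the sampling noise of two small escalations.

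Much of this stands. The harm needs someone to follow the Cohort 2 sentence, and the percentages do not say how likely that is. The missing carry-over is an omission, not a contradiction in itself. But the bar on rejected levels is one more rule that reading (a) conflicts with; it does not reconcile the text. The documents available contain no statement that section 4 prevails over section 11.

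A third reading, that the sentence loosely restates the 300 mg entry dose for phase I, would remove the conflict. It does not fit: the sentence stands under Phase II, and its Cohort 1 counterpart gives the phase II dose.

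**Conclusion.** The concern holds. The Cohort 2 sentence gives a phase II dosing rule that conflicts with 4.1.4, 4.1.1.7 and the rest of 11.2, and it agrees with them only if the doses happen to coincide. That conclusion rests on the text and on 2×18 + 2×22 = 80, and needs no assumption about toxicity.

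The size is illustrative. If both cohorts share one of the six assumed curves, the two rules give different doses in 14% to 70% of cases on reading (a). The relapsed MTD is higher in 8% to 44%; across the curves, 3% to 29% is a dose the frontline escalation rejected and 3% to 17% one it never tested. On reading (b), the frontline MTD is above 300 mg in 45% to 96% of cases and below it in 1% to 20%. Very low toxicity makes reading (a) almost harmless. The design calculations are unaffected. This should be corrected, but it does not undermine the trial, because the intended rule is clear elsewhere.

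**What to change.** In 11.2, Phase II, Cohort 2, replace the first sentence with wording such as: *Phase II in this cohort starts once its own phase I has set the MTD (or has reached bosutinib 500 mg without exceeding it), and its patients receive bosutinib at that dose.* After the total of 28, add: *(counting the 6 frontline phase I patients treated at that dose)*.

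The cost is one sentence and one parenthesis. The maximum of 80, the Simon rule with its error rates, and the safety boundary all stay the same.
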